## **Investigator Help**

- 9.1. **Primary objective (or aim):** To evaluate the effectiveness of the SPARCK intervention in increasing vaccine acceptance.
- 9.2. **Secondary objectives (or aims): (1)** To assess how parent-rated experience of the vaccine discussion changes as a function of the SPARCK intervention and **(2)** to characterize the effect of the SPARCK intervention on provider perceptions of barriers to quality vaccine discussions.
- 9.3. Outcome measures and rationale for selection: The primary outcome measure will be child's immunization status at 8 months of age. Our secondary outcomes will be (1) parent ratings of their visit experience and vaccine discussion with their child's provider after the 6 month health supervision and (2) pre- and post-study provider perceptions of barriers to quality vaccine discussions with parents. These outcomes will allow us to measure the effectiveness of the SPARCK intervention.

#### 10. Study Medication / Study Intervention

- 10.1. **Describe the study medication or study intervention (if applicable).** Parent participants randomized to the intervention arm will receive the intervention survey (within which the PACV is embedded) before their child's 2 and 6 month health supervision visits (Appendix A). These results will be communicated to their child's provider in paper form (Appendix C) before the provider enters the exam room for each of these visits.
- 10.2. Describe the study agent (include dosing and rationale for dosing) or study intervention (include who will provide the intervention/therapy, when and where, as applicable). Parents will complete the intervention survey (Appendix A) on a study iPad® in their child's clinic prior to their child's 2 and 6 month health supervision visits.
- 10.3. Describe treatment compliance and adherence assessment. N/A

Study Title: Screening Parents about Recommended

Care for Kids (SPARCK) Study

Principal Investigator: [name], MPH

[figure not shown]
**Version Date: 5/1/2018** 

#### **Investigator Help**

## 11. Investigational Plan

## 11.1. Describe the general schema of the study design.

Figure 1. Study Design

This study is a cluster randomized controlled trial. We will pair up to 30 Seattle area primary care clinics and Group Health primary care clinics based upon the number of vaccine doses ordered and enroll and randomize clinics to control and SPARCK arms. We will screen parents for vaccine hesitancy using the Parent Attitudes about Childhood Vaccines Short Form survey (PACV-SF) (Appendix F). Parents in the SPARCK arm of the study will take the intervention survey (which has the PACV embedded in it) to their child's 2 and 6 month visits (Appendix A) whereas parents in the control arm of the study will take a placebo survey about childhood health topics (Appendix B). The results of these surveys will be communicated to the child's provider (Appendices C and D). After the child's 6 month visit, parents in both arms will complete a satisfaction survey about their visit experience (Appendix E). When the child is 8 months of age, we will use an automated clinic immunization database to determine their immunization status. For participants who were lost to follow up (i.e. those who did not have a 6 month appointment, or those who did not have a 2 and 6 month appointment), we will also use Washington State Immunization information System records to determine participant immunization status.

Study Title: Screening Parents about Recommended

Care for Kids (SPARCK) Study

Principal Investigator: [name], MPH

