**Version Date: 5/1/2018** 

Name of Questionnaire/Instrument	How will the questionnaire/instrument be administered? (Examples: study personnel, self-administered, computer, etc.)	Who answers the questionnaire? (Examples: parent, child)	If modified after initial approval, note current revision date:
Parent SPARCK intervention survey (Appendix A)	Self-administered on iPad®	Parent	
Parent SPARCK Placebo Survey (Appendix B)	Self-administered on iPad®	Parent	
Parent post-visit satisfaction survey (Appendix E)	Self-administered on paper	Parent	
Parent Eligibility Survey (Appendix F)	Study personnel verbally	Parent	
Parent demographic survey (Appendix G)	Self-administered on paper	Parent	
Provider Baseline Survey (Appendix K)	Self-administered electronically	Provider	
Provider Follow-Up Survey (Appendix L)	Self-administered electronically	Provider	
Vaccine data collection form for Allegro Pediatrics sites	Study personnel	Study personnel	

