#### **Analysis Plan and Statistical Methods**

16.1. Outline the data analysis plans relating to each specific aim/objective or research hypothesis mentioned in section 11 above. It should be clear how the analysis results will allow each aim/objective to be answered. The analysis plans for the primary aim should be detailed. Analysis plans for secondary aims may be brief, but must be included. Give the names of specific statistical methods and state which variables will be used with them.

Aim1: To evaluate the effectiveness of the SPARCK intervention in increasing vaccine acceptance. We will conduct an intention-to-treat analysis for Aim 1. Parents will be the unit of analysis. We will examine baseline characteristics among control and SPARCK parents using Pearson's  $\chi 2$  tests (or Fisher's exact tests) for categorical variables and t-tests for continuous variables to assess for any unbalanced confounders between control and SPARCK arms. To compare our primary outcome of percent days underimmunized between control and SPARCK arms, we will apply linear mixed effects regression modeling to the percent days under-immunized with clinic-specific random-effects to account for within-clinic correlation. If unbalanced confounders are detected between arms, they will be adjusted for in the mixed effects models.

Aim 2: To assess how parent-rated experience of the vaccine discussion changes as a function of the SPARCK intervention. For Aim 2, we will use Pearson's χ2 test to compare parent (binary) ratings of their vaccine discussion between control and SPARCK

Study Title: Screening Parents about Recommended

Care for Kids (SPARCK) Study

Principal Investigator: [name], MPH

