## 16.2. Provide a justification for the sample size and power calculations.

Based on preliminary data, children of parents with a positive PACV-SF had a mean percentage of days under-immunized of 27.1% (standard deviation [SD] 33.3) from birth to 8 months of age for 4 vaccines combined (hepatitis B, DTaP, Hib, and IPV). To be able to detect with adequate power (90%) a decrease in under-immunization of 30 days per vaccine—a decrease that has the potential to be clinical meaningful since it equals the 1 month recommended interval a parent has before their child is considered late for a vaccination dose—we need to enroll 160 parent/newborn pairs total, with 80 per arm and 10 at each of the 16 study clinics (assuming an  $\alpha$  of 0.05 and an intraclass correlation coefficient for within-clinic correlation of 0.02).

In our original calculation, we assumed 80% of GH parents would be reached, a conservative estimate of a 20% prevalence of GH parents who will have a positive PACV-SF, 10% of VHPs who fail to meet other study eligibility requirements, 25% of VHPs who do not agree to participate (unpublished data), a 10% attrition rate over the course of the study, and 70% who remain continuous GH members, resulting in the need to approach 2400 parents to reach our sample size goal. From 2010 – 2012, there was an average of 2679 GH births per year in the 5 Washington State counties from which we will recruit parents. Reaching our sample size goal should therefore be feasible given our designated 15 month recruitment period. However, we now know that the vaccine hesitancy rate at GH is about 5%. Therefore, we need to screen approximately 3500 parents to reach the desired sample size goals of 160.

For Aim 2, we will have 80% power with a sample size of 160 parents to detect a 17% increase in the proportion of parents who rate their visit highly, assuming a baseline proportion of 72%.  For Aim 3, we will have 80% power to detect a 14% pre-post difference in the proportion of providers who perceive time as a barrier to quality vaccine discussions between control (1% pre-post difference) and SPARCK arms (15% pre-post difference), assuming a baseline proportion of 62% and 56 providers in each arm.

Study Title: Screening Parents about Recommended

Care for Kids (SPARCK) Study

Principal Investigator: [name], MPH

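### The state registry is added only for children who miss study appointments, so doses given elsewhere to retained children may be missed in the primary outcome

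*Combined protocol and SAP*

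**What the plan says.** Section 11.1 gives one main source for the outcome: "When the child is 8 months of age, we will use an automated clinic immunization database to determine their immunization status". A second source is conditional. It begins "For participants who were lost to follow up (i.e. those who did not have a 6 month appointment", goes on to a second limb that names the 2 and 6 month visits together, and concludes that "we will also use Washington State Immunization information System records to determine participant immunization status". No other section extends the registry search to children who keep their appointments.

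The instrument list in section 5.2 also has an entry completed by study personnel, "Vaccine data collection form for Allegro Pediatrics sites". Its content is not described in the text.

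Section 16.1 states "We will conduct an intention-to-treat analysis for Aim 1" and compares the "primary outcome of percent days underimmunized between control and SPARCK arms" with a linear mixed model. Section 11.10 treats withdrawals as missing data, and section 16.3 excludes missing data.

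**The concern.** Including the registry as a fallback implies that the clinic record can be incomplete. The trigger for using it is appointment attendance, which occurs after randomisation and only partly tracks which records are incomplete. Two children with the same doses from the same outside clinic can get different outcome values because one kept the 6 month appointment and the other did not.

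The clearest case is a family that attends at 6 months, defers doses, changes clinic and has them given before 8 months. A second is a family that attends the study visits but has some doses given elsewhere. In either case, if the clinic source does not hold the outside doses, the child accrues under-immunized days that did not occur.

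An arm difference is plausible on the protocol's own account. Section 15.1 lists strain on the relationship between parent and provider as a risk, and says that disclosing hesitancy may bring disagreement into the open. Providers receive the hesitancy score and item responses only in the SPARCK arm; control providers receive results of a placebo survey on health topics. If this changes where families go, or whether they attend, the arms could differ in how completely doses are captured.

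**Working it through.** **Sources by type of child, as section 11.1 reads**

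| Child | Source of dose dates |
|---|---|
| Keeps both the 2 and 6 month appointments | Clinic source only |
| Attends at 6 months, then changes clinic | Clinic source only |
| No 6 month appointment | Clinic source plus registry |
| Misses only the 2 month visit | Unclear from the wording |

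The rule is the same in both arms, but the set of children it selects is determined after randomisation.

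**Target effect in points.** Section 16.2 gives 30 days per vaccine, from birth to 8 months, for four vaccines. Taking 8 months as about 243.5 days (my conversion), 30 / 243.5 = 12.3 points. With 240 days it is 12.5.

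**False days per affected child.** Assumptions: three of the four vaccines are affected; the outside doses were in fact on time; a missed dose counts as late from one month after it was due (the interval in section 16.2) and stays late to 8 months. The total is 4 × 243.5 = 974 vaccine-days.
- Doses due at 6 months, late from 7 to 8 months: 3 × 30.4 / 974 = 9.4 points.
- Doses due at 4 months, late from 5 to 8 months: 3 × 91.3 / 974 = 28.1 points.

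The first figure fits a family that leaves after the 6 month visit, and is smaller if the outside doses came after 7 months. The second does not follow from leaving after 6 months. It needs doses given elsewhere at about 4 months to a child who still attends study visits.

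**Shift in the contrast.** Shift = arm difference in share affected × false points per affected child.

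| Arm difference in share affected (assumed) | At 9.4 points | At 28.1 points |
|---|---|---|
| 2 points | 0.2 | 0.6 |
| 5 points | 0.5 | 1.4 |
| 10 points | 0.9 | 2.8 |

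The last row is about 8% to 23% of the 12.3-point target (0.94 / 12.3 and 2.81 / 12.3).

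**Shift through attendance alone.** Suppose outside doses are equally common in both arms but loss to follow-up differs by 10 points. The arm with more loss has more children searched in the registry, and so fewer false days. With 2% to 10% of children having outside doses and 25 to 50 false points each (all assumed), the shift is 0.10 × 0.02 × 25 = 0.05 to 0.10 × 0.10 × 50 = 0.5 points.

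**Equal misses in both arms.** If 10% are affected in each arm, both means rise by 0.9 to 2.8 points and the contrast is unchanged. If false days are unrelated to true values, the added variance is 0.10 × 0.90 × 9.4² = 8.0 or 0.10 × 0.90 × 28.1² = 71.1. Against 33.3² = 1108.9 (SD from section 16.2), that is about 0.7% or 6%.

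**The case against.** The strongest reply is that a clinic immunization database may already hold doses given elsewhere, entered as history or imported. The documents do not say. If it does, little is lost. A reader might infer from section 11.1 that retained children with outside doses are necessarily scored as under-immunized; the text supports only that such doses may be missed. The outcome is also continuous, so a missed dose adds days and does not reclassify the child.

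The trigger is also sensible as far as it goes. A child with no 6 month appointment is likely to have one of the least complete clinic records, and the registry recovers outcomes that would otherwise be poor or missing. The rule is identical in both arms, so bias needs an arm difference that the documents make plausible but do not quantify. Both points stand, and they limit the severity.

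Three further inferences are tempting and should not be drawn:
- **That a child who missed only the 2 month visit is excluded from the registry search.** If the second limb of the definition means neither visit, it is redundant, since the first limb already covers those children. Read as not both visits, it includes this child. The wording is unclear, no more.
- **That 30% of families have truncated records, because section 16.2 assumes "70% who remain continuous GH members".** That factor applies to Group Health only, its time window is not stated, and it belongs to the recruitment arithmetic: 2400 × 0.8 × 0.2 × 0.9 × 0.75 × 0.9 × 0.7 = 163. The target of 160 is thus already net of leavers, so the figure gives no share of analysed children with incomplete records.
- **That the form at one clinic group is a differently ascertained third source.** It may simply be the tool for abstracting the clinic record there.

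**Conclusion.** The point holds as a design weakness that should be fixed. Under section 11.1, whether an outside dose can be found for the primary outcome depends in part on attendance after randomisation, and no other section corrects this.

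The size is unknown. The shift of 0.9 to 2.8 points against a target of about 12 rests on assumed values for the vaccines affected, the length of the false delay and a 10-point arm difference in the share affected; the documents give no frequency of outside doses. Smaller arm differences give shifts well under 1.5 points, and no arm difference gives no bias. The direction is also open: more missed outside doses in the SPARCK arm would understate a benefit, and more in the control arm would overstate it. A claim that the primary comparison is invalid would go beyond the documents. The case for acting is that a uniform rule removes the dependence on attendance at little cost.

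**What to change.** In section 11.1, remove the lost-to-follow-up condition. For every enrolled child whose records may be used, in both arms, take dose dates from the clinic record (or the abstraction form) plus the state registry, de-duplicated by vaccine and date, through 8 months of age. State whether the clinic database and the form hold doses given elsewhere. In section 16.1, add a sensitivity analysis using the clinic record alone for all children, which will show how much the registry changes the result. State how the rule fits with sections 11.10 and 16.3, so that a child with registry data is not dropped as missing merely for having missed a visit.

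The cost is registry look-ups for about 160 children instead of a subset, some matching and de-duplication, and possibly a small IRB modification. Registry access is already planned, and the sample size does not change.

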**Version Date: 5/1/2018** 

#### **Investigator Help**

#### **Trial Phases**

11.2. Describe the trial phases (if applicable). N/A

#### **Control Group**

11.3. **Describe the control group (if applicable).** Parents in the control arm will receive a placebo survey that asks questions about their attitudes about childhood health topics (Appendix B). These results will be conveyed to their child's provider (Appendix D).

#### Randomization Method and Blinding

11.4. Describe the randomization method and blinding (if applicable).

Among interested Seattle area primary care practices and 21 Group Health primary care clinics in 5 western Washington counties (King, Snohomish, Pierce, Thurston, and Kitsap), we will pair clinics based upon the number of vaccines doses ordered in the prior year and subsequently enroll and randomize up to 30 to the control and SPARCK intervention arms. We will conceal study arm allocation and describe the study generally as one that seeks to determine the impact of soliciting parent attitudes regarding preventive care topics before health supervision visits on improved health outcomes.

#### **Investigator Help**

#### Plan for Non-Responders

- 11.5. Describe the plan for non-responders (if applicable). N/A
- 11.6. Define who will be considered a "non-responder". N/A
- 11.7. Describe the alternative therapy non-responders will be transitioned to, the rationale for that therapy, and when they will be transitioned to the alternative. N/A
- 11.8. Explain how non-responders will be followed and for what variables. N/A
- 11.9. Discuss risks of transition and measures taken to minimize risks. N/A

#### **Early Withdrawal of Participants**

11.10. Describe potential reasons for withdrawal, plan for tracking withdrawals, how participants' safety will be assessed in response to withdrawal, plan for follow up of withdrawn participants.

Parents and providers may withdraw at any time. A wish to no longer spend time filling out surveys may be the reason that parents and providers withdraw. If parents or providers withdraw before the study ends, we will consider this as missing data. We will

Study Title: Screening Parents about Recommended

Care for Kids (SPARCK) Study

Principal Investigator: [name], MPH

**Version Date: 5/1/2018** 

not follow up with withdrawn participants. Our sample size and power calculations account for this expected attrition.

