#### The specific aims of this project are as follows:

Aim 1: Evaluate the impact of the SPARCK intervention on a child's immunization status. We will use a matched-pair, cluster randomized controlled trial design in which we assign up to 30 primary care clinics in the Seattle area and within the Group Health healthcare delivery system in Western Washington to a control arm or the SPARCK arm and enroll 160 vaccine-hesitant parents whose newborns receive health supervision at study clinics.

Aim 2: Assess how parents' ratings of their vaccine discussions with their child's provider change as a function of the SPARCK intervention. This will be accomplished by

Study Title: Screening Parents about Recommended

Care for Kids (SPARCK) Study

Principal Investigator: [name], MPH

Version Date: 5/1/2018

assessing parent visit satisfaction with a questionnaire after their child's 6 month health supervision visit.

Aim 3: Compare pre- and post-study perceptions of barriers to quality vaccine discussions with parents between providers in the SPARCK and control arm. This will be accomplished by having providers complete a survey assessing their perceptions of specific barriers to quality preventive care discussions with parents before the study begins and then again after the study ends.

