**Version Date: 5/1/2018** 

16.3. **Describe how missing data will be handled.** Missing data will be excluded from analysis.

- 16.4. Describe plans for interim analysis and early stopping rules (if applicable). N/A
- 16.5. Describe under what circumstances will un-blinding occur and the procedures to do so (if applicable). N/A

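### The plan uses 160 as the number to enrol and as the number behind the stated power, while its recruitment arithmetic treats 160 as the number left after losses, so the claim that attrition is covered is not borne out for the enrolment target or the power

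*Combined protocol and SAP*

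**What the plan says.** Section 11.10 treats parents who withdraw as missing data, does not follow them up, and adds: "Our sample size and power calculations account for this expected attrition". Section 16.3 then states: "Missing data will be excluded from analysis".

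Three places give 160 as an enrolment figure:
- Section 1.1, Aim 1: "enroll 160 vaccine-hesitant parents whose newborns receive health supervision at study clinics".
- The table in section 2.1, which shows about 160 in the enrolment column.
- Section 16.2, for 90% power on Aim 1: "we need to enroll 160 parent/newborn pairs total, with 80 per arm and 10 at each of the 16 study clinics".

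For Aim 2, section 16.2 says "we will have 80% power with a sample size of 160 parents to detect a 17% increase", "assuming a baseline proportion of 72"%. Neither power statement contains a term for losses.

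Losses appear in the next step of 16.2, the count of parents to approach. That list includes "a 10% attrition rate over the course of the study, and 70% who remain continuous GH members" and ends at 2400 parents. The section then reports a hesitancy rate of about 5% at Group Health and raises the number to screen to about 3500.

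Section 11.1 adds that state immunization registry records will be used for participants who missed the 6 month visit, or both the 2 and 6 month visits.

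**The concern.** One number is doing two jobs. If 160 is the enrolment ceiling, the analysed sample will be smaller than the sample on which the stated powers rest. If 160 is the analysable number, the enrolment figures in 1.1, 2.1 and 16.2 are too low. The sentence in 11.10 hides the choice, because a reader would conclude that recruitment can safely stop at 160 and that withdrawals have already been paid for. At stake are a few points of power for each aim and a clear rule for when enrolment is complete.

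**Working it through.** **Inputs, all from 16.2.** Reach 80%; positive short-form screen 20% (original) or about 5% (revised, stated for Group Health); ineligible 10%; declining 25%; attrition 10%; continuous Group Health membership 70%; ICC 0.02; 16 clinics of 10; 80 per arm; alpha 0.05. Sidedness is not stated, so two-sided is assumed. The Aim 2 increase is read as 72% to 89%.

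**1. Reproducing 2400.**
- Enrolled: 2400 × 0.8 × 0.2 × 0.9 × 0.75 = 259.
- Retained: 259.2 × 0.9 × 0.7 = 163.
- Working back from 160 retained: 160 / (0.8 × 0.2 × 0.9 × 0.75 × 0.9 × 0.7) = 2352, close to 2400.
- Without the attrition term: 160 / (0.8 × 0.2 × 0.9 × 0.75 × 0.7) = 2116.
- Without attrition or membership loss: 160 / (0.8 × 0.2 × 0.9 × 0.75) = 1481.

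So 2400 carries both losses, and in this arithmetic 160 is a retained number that comes from about 259 enrolled.

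**2. The revised 3500.** Taking 5% throughout (an assumption, since the rate is given only for Group Health) and treating all 3500 as reached: 3500 × 0.05 = 175 hesitant, and × 0.9 × 0.75 = 118 enrolled, before any attrition. The revision does not visibly keep the allowance that 2400 contained.

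**3. Numbers analysed and enrolled.** If 160 are enrolled: 160 × 0.9 = 144, or 72 per arm and 9 per clinic. If 160 must be analysed: 160 / 0.9 = 178 enrolled.

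**4. Aim 1: the part due to attrition.** To isolate it, take the stated 90% as correct at 80 per arm.
- The design effect is 1 + (m − 1) × 0.02: 1.18 at m = 10 and 1.16 at m = 9.
- Effective size per arm: 80 / 1.18 = 67.8 and 72 / 1.16 = 62.1.
- At 90% power the effect divided by its standard error is 1.960 + 1.2815 = 3.2415.
- After the loss: 3.2415 × √(62.1 / 67.8) = 3.102.
- Power = Φ(3.102 − 1.960) = 87.3%.

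The clinic count hardly matters to this step. With 30 clinics the design effects are 1.087 and 1.076, and 3.2415 × √(66.9 / 73.6) = 3.090, which gives 87.1%.

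**5. Aim 2, no clustering.** Power = Φ{[0.17√n − 1.96√(2p̄(1 − p̄))] / √(p₁(1 − p₁) + p₂(1 − p₂))}, with p₁ = 0.72, p₂ = 0.89 and p̄ = 0.805. The two roots are 0.560 and 0.547.
- n = 80: Φ(0.772) = 78.0%, within 2 points of the stated 80%. The stated figure therefore treats all 160 as analysed.
- n = 72: Φ(0.629) = 73.5%.

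**The case against.** The best defence is that attrition was counted. The 10% stands inside the sample size section, 2400 reproduces only with it, and the section calls the result its sample size goal. On that reading 160 is the retained number, power is computed on the analysable sample, and the fault is a loose use of the word for enrolment in three places. Part of this stands. A reader might infer that the sentence in 11.10 is simply untrue, and the documents do not support that. They do show that an approach count is the only place where attrition enters. The sentence names the sample size and the power, and neither shows it.

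A reader might also apply the 30% membership loss and conclude that about 101 would be analysed (160 × 0.9 × 0.7), or that about 254 must be enrolled (160 / 0.63). This does not follow from 11.10, for three reasons:
- That section concerns withdrawals, whereas membership loss is a separate term in 16.2.
- The 70% is a rate for Group Health members, and the trial also recruits at other Seattle-area clinics.
- Registry records under 11.1 can supply immunization status for children who missed visits.

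The registry point also limits the 10% figure for Aim 1. The plan does not split attrition into withdrawals and missed visits, and registry data can cover the second group, so 144 is a lower bound. The registry cannot supply the Aim 2 visit ratings.

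**Conclusion.** The inconsistency holds. The plan states 160 as the enrolment target and powers Aims 1 and 2 on the same 160, while its own recruitment arithmetic makes 160 the number left from about 259 enrolled. The claim in 11.10 is not supported for the enrolment target or for the power.

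The effect is modest and conditional on enrolment stopping at 160. At most it moves Aim 1 from a true 90% to about 87%, and Aim 2 from about 78% to about 74% without clustering. It disappears if 160 means analysed pairs and recruitment continues accordingly. The figures assume 10% loss spread evenly over clinics and a two-sided 5% test.

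Two larger shortfalls should not be attributed to attrition. The stated 90% does not reproduce from SD 33.3 and 30 days: with 8 months taken as about 243 days, power is about 58% at 160, and 10% attrition takes it only to about 54%. The Aim 2 power also appears to contain no allowance for clustering. Both are separate points.

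**What to change.** State once, and use consistently in 1.1, 2.1, 11.10 and 16.2, whether 160 is the number enrolled or the number analysed.

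- **If enrolled:** correct the sentence in 11.10 and restate the Aim 1 and Aim 2 powers for about 144 analysed. Note that 144 is a worst case for Aim 1 because of the registry. This costs wording and a slightly lower stated power, with no extra participants.
- **If analysed:** replace the enrolment figure with the one that the plan's loss rate implies, about 178 at 10%, which is 18 more pairs. Show any allowance for membership loss separately and for Group Health parents only.

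In either case, show the steps behind 3500 so that a reader can see whether attrition is still in it.
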